After 24 intervention sessions, patients are invited for the post-intervention assessment. This assessment will be scheduled as close as possible to the last training session. Participants will first evaluate the intervention with a non-blinded study member. Directly afterwards, participants will undergo a post-intervention assessment ('T1'). This assessment comprises a neuropsychological assessment and questionnaires (see Table 2). One team member (TB) will be de-blinded after the last T1 visit. All assessments after baseline will make use of parallel versions of neuropsychological tasks, if possible.

After six months ('T2'), one year ('T3') and two years ('T4'), participants will again undergo an extensive neuropsychological assessment and questionnaires. At T3 and T4, motor symptoms will also be assessed. From T3 onwards will be a naturalistic follow-up.

Blinding

Outcome assessors will be blinded for the full length of their role as assessor, while non-blinded team members will not assess participants at any point in this study. Blinded study members will not have access to the key of the randomization. Trial participants will be blinded for the full length of the study. Participants will be asked not to share any details of their intervention with the outcome assessor at any point in the study. When the participants' condition is revealed to an outcome assessor, he or she will be replaced by another assessor for this participant.

Drop-outs

Participants that drop out of the study after being allocated to an intervention condition will not be replaced. We expect a low drop-out rate on the basis of our pilot study (one drop-out in 21 participants) and the low burden and short duration of both training conditions. In our sample size calculation, we conservatively account for 10% drop-out.

In case a participant withdraws from the study after four weeks of training (or more), we will aim to schedule an exit-measurement to measure the intervention effect.

Medication adjustments

Participants and their neurologist will be requested to retain a stable medication regime during the study period, specifically during the intervention. Patients and their neurologist will be requested to inform the study team if medication changes are clinically necessary.

Table 2 Tabular overview of the study time schedule including assessments and visits.

Time-point	T-2	T-1	T0	T1	T2	T3	T4
Pre-screening							
Informed consent for pre-screening		X					
SAGE	X						

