- Data on physical activity at each visit will be measured by the New Zealand Physical Activity Questionnaire – Short Form, a structured interview on mild, moderate and vigorous physical activity, as physical activity is known to positively influence cognitive function and potentially provide a neuroprotective effect.[69, 70];
- We will rate motor symptom severity by the Unified Parkinson's Disease – Rating Scale part III and assess disease stage by the modified Hoehn & Yahr stage [71];
- Medication usage data are collected and transformed into a 'levodopa equivalent daily dosage' [33]. Dopamine replacement therapy may influence cognitive functions [72, 73];
- Intervention compliance will automatically be monitored by the training module. We will calculate total compliance as the proportion of completed training games out of 24 total sessions: $[N_{\text{completed}} / N_{\text{total}}] \times 100\%$, in which N_{total} is 13 games x 24 sessions in the CT

condition, and 3 games x 24 sessions in the AC condition. We define non-compliance as a completion rate lower than 75%, in accordance with Petrelli and colleagues [74].

ANALYSIS PLAN

Data-analyses will be performed on the Modified-Intention-To-Treat population, which comprises the compliant participants that underwent at least 75% of the intervention and at least one post-training assessment. We will compare the baseline characteristics of this sample to the Intention-to-Treat population (all randomized subjects). Secondary Per Protocol-analyses will be performed comprising the population that underwent the complete study protocol. Analyses will be performed with IBM SPSS version 22 (Armonk, NY, USA) and in R [75]. We will employ a statistical threshold of $\alpha = .05$.

The primary outcome will be analyzed using a multivariate mixed-model analysis using the accuracy on the five separate task-loadings (S1-S5) of the ToL at post-training visit (T1) as dependent measures, the training condition (CT vs. AC) as independent measure and baseline score of the outcome measures as covariates. We will construct a separate adjusted model with age, sex and years of education as additional covariates of no-interest. No imputation of missing values will be performed as this is not needed in linear mixed models.

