The secondary outcome measures will also be analyzed with linear mixed-models with baseline score of the outcome measures as covariates. Subjective cognitive dysfunction will be modeled with the total score of the PD-CFRS (both self-report and caregiver) and the CFQ a) at post-training (T1) and b) at all follow-up assessments (T2, T3 and T4) as dependent variables. We will perform a factor analysis on all neuropsychological assessment outcomes (see Table 2) at baseline using a factor analysis with regularized maximum likelihood estimation to produce latent cognitive traits. We will compute baseline trait scores (i.e. factor scores), and compute trait scores at follow-up measurements based on the baseline factor analysis. The effect of CT on cognitive functions will be assessed with a multivariate mixed-model comparable to the above, using the trait scores as dependent variables. The effect of CT relative to AC on neuropsychiatric symptoms will be analyzed using similar multivariate mixed-models with as dependent variables the Beck Depression Inventory, the Parkinson Anxiety Scale, the Apathy Scale and the Questionnaire for Impulsive-Compulsive Disorders in Parkinson's Disease – Rating Scale. Covariates will be added to the regression model based on a change-in-estimate method if there is a change of $\geq 10\%$ of the regression coefficient for the intervention variable.

In order to analyze between-group differences in conversion to PD-MCI or PD-D, we will first classify patients at baseline, T3 and T4 as having normal cognition, PD-MCI or PD-D. We define conversion 'down' as conversion to a milder cognitive dysfunction classification, no conversion as classification in the same category at a later assessment visit and conversion

'up' as conversion to a worse cognitive function classification. We will assess the association between the intervention and conversion rate with a Fisher's exact test. Odds ratios and confidence intervals of the conversion 'down' and no conversion groups versus the conversion 'up' group will be computed as a measure of effect size.

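### The PD-CFRS and CFQ follow-up model appears to leave out T1, so the reason given for not imputing holds only in part

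*Combined protocol and SAP*

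**What the plan says.** All places are in the combined protocol and SAP.

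- **Analysis plan, secondary outcomes.** The general rule is "The secondary outcome measures will also be analyzed with linear mixed-models with baseline score of the outcome measures as covariates". For PD-CFRS and CFQ the dependent variables are the scores "a) at post-training (T1) and b) at all follow-up assessments (T2, T3 and T4) as dependent variables". The plan does not say outright that (a) and (b) are different models, but that is how the sentence reads.
- **Analysis plan, latent cognitive traits.** "The effect of CT on cognitive functions will be assessed with a multivariate mixed-model comparable to the above, using the trait scores as dependent variables". No visit structure is given. The neuropsychiatric scales are treated the same way.
- **Analysis plan, primary outcome.** The dependent variables are "accuracy on the five separate task-loadings (S1-S5) of the ToL at post-training visit (T1) as dependent measures". The missing-data sentence stands in this paragraph: "No imputation of missing values will be performed as this is not needed in linear mixed models". It reaches the secondary outcomes because they too get linear mixed models.
- **Analysis plan, population.** The modified intention-to-treat set "comprises the compliant participants that underwent at least 75% of the intervention and at least one post-training assessment".
- **Post-intervention assessments.** "After six months ('T2'), one year ('T3') and two years ('T4'), participants will again undergo an extensive neuropsychological assessment and questionnaires".

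The plan states neither a missing-at-random assumption nor a sensitivity analysis for missing data.

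**The concern.** A likelihood-based mixed model can stand in for imputation because a person's other observed outcomes carry information about the missing ones. It can use only the outcomes that are in the model.

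In model (b), someone seen at T1 and never again belongs to the analysis set, which asks for "at least one post-training assessment", yet contributes nothing. If the T1 result influenced who left, and did so differently by arm, model (b) cannot correct for it although the T1 score is on file. In model (a), a single scale has one dependent visit. A participant who misses T1 but attends T2 is in the set and contributes nothing to (a).

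Durability at six months, one year and two years is a secondary objective with its own hypothesis, and model (b) is what tests it for subjective complaints.

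**Working it through.** **Step 1. The plan's own design figure.** The Sample size section gives f = 0.12, r about 0.6, alpha 0.05, N = 112; I read the printed beta of .8 as power. For the group-by-time test in a two-group, two-occasion repeated-measures ANOVA, lambda = f² × N × m / (1 - r) = 0.0144 × 112 × 2 / 0.4 = 8.06 on 1 and 110 df. Power is 0.804; at N = 110 it is 0.796. So 112 is reproduced. This concern disputes no stated number; the section only supplies planning values (g = 0.23, r about 0.6, drop-out 10%).

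**Step 2. What model (b) loses, by formula.** Assume equal correlation r between all visits and unit variance. Given baseline, the slope of a later visit on T1 is r(1 - r)/(1 - r²) = r/(1 + r), which is 0.375 at r = 0.6. If selection after T1 shifts the baseline-adjusted T1 contrast among stayers by d, model (b) is biased by d × r/(1 + r). A model that includes T1 removes this term.

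**Step 3. Simulation.** Assumptions not in the documents:

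- equal correlations of 0.5, 0.6 or 0.7;
- a constant effect of 0.23 SD, scored so that higher is better;
- all loss between T1 and T2;
- logistic loss with slope -1.5 per SD of the T1 score;
- overall loss of 10, 20 or 30%.

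Bias comes from 2,000,000 simulated subjects per scenario (Monte Carlo error about 0.001). Ranges are over r.

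| Loss after T1 | Bias of (b), T1 drives loss in CT only | Bias of (b), T1 drives loss equally in both arms |
|---|---|---|
| 10% | +0.030 to +0.034 | -0.006 to -0.009 |
| 20% | +0.053 to +0.063 | -0.011 to -0.012 |
| 30% | +0.077 to +0.084 | -0.012 to -0.015 |

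The joint T1-T4 model stays within 0.004 SD of the truth in every scenario. Repeat runs varied slightly: about +0.02 to +0.03 at 10% and +0.07 to +0.08 at 30%. When the 10% loss is confined to the CT arm, I get +0.027 to +0.031.

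Check against Step 2, at r = 0.6 and 10% loss: d = 0.0917, and 0.0917 × 0.375 = 0.034.

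**Step 4. Scale.** Relative to 0.23: 0.03/0.23 = 13%, 0.06/0.23 = 26%, 0.08/0.23 = 35%. The standard error was simulated with 126 participants at T1 (140 × 0.9) and 3,000 repetitions. At r = 0.6 and 10% completely random loss it is 0.156 for (b) and 0.155 for the joint model. So 0.03 SD is about one fifth of a standard error (0.03/0.155 = 0.19).

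**Step 5. What the planned models already protect against.**

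- Loss after T2 that depends on T2 in the CT arm: model (b) has bias of about 0 for the T4 effect, against +0.030 to +0.083 for a T4-only analysis at 10 to 30% loss.
- T1 missing for about 11%, driven by baseline differently by arm (r = 0.6): the T1 model has bias of about 0.002, because baseline is a covariate.
- Completely random loss: neither model is biased.
- The same total loss spread over the three follow-up gaps, each driven by the last observed score in the CT arm (r = 0.6): bias of (b) is about +0.01 at 10% and +0.02 at 20%.

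**The case against.** A reader might infer that the mixed models give no protection at all. The documents do not support that. Model (b) has three repeated visits and a baseline covariate, and Step 5 shows it correcting fully for loss driven by T2. Jointly modelled scales could also share information at one visit, though a missed visit usually loses them together.

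A reader might also infer that every secondary outcome is split this way. The split is written only for PD-CFRS and CFQ; for the trait scores and neuropsychiatric scales the visit structure is open, and conversion is tested with Fisher's exact test.

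On size, the larger figures need loss concentrated straight after T1 and driven by T1 in one arm only. Nothing in the documents predicts this: participants are to be blinded and the control is active. The planned loss is 10%. That figure, however, rests on a pilot with one drop-out in 21 and on the short, low-burden training, and no visit-specific rate is given for the two-year follow-up. Higher loss therefore cannot be excluded.

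A missed T1 visit followed by later attendance should be uncommon among compliant participants, since T1 is scheduled close to the last session. Finally, one team member is de-blinded after the last T1 visit, which fits an early T1 report. That is a reason to keep the T1 analysis, not a reason to leave T1 out of the later model.

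These points limit the size and reach of the concern. They do not supply a reason for omitting T1 from the follow-up model.

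**Conclusion.** The point holds in a limited form. On the natural reading, the PD-CFRS and CFQ follow-up model does not use T1, so the blanket statement that imputation is unnecessary is too strong. Protection is partial: present across T2-T4 and through baseline, absent for loss driven by the T1 result, and absent in a single-scale T1 model when the T1 visit is missed for reasons other than baseline.

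Under the Step 3 assumptions with CT-only dependence, the bias is about +0.02 to +0.03 SD at 10% loss, +0.05 to +0.06 at 20% and +0.07 to +0.08 at 30%. It is about -0.01 SD if the dependence is equal in both arms, and smaller if loss is spread over follow-up. At the planned 10% it is small beside a standard error of about 0.155.

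This does not show that the durability result will be wrong, and it does not bear on the primary Tower of London analysis or on the stated sample size. It is a cheap improvement with data already being collected.

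**What to change.** For PD-CFRS and CFQ, and for the trait scores when their follow-up is modelled, fit one longitudinal mixed model per scale. Use T1, T2, T3 and T4 as dependent visits, with arm-by-visit and baseline-by-visit terms and an unstructured visit covariance, and read the T2-T4 contrasts from it. Replace the sentence saying imputation is not needed with a statement that the analysis assumes data missing at random given the observed baseline and post-training scores in the model.

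The T1 analysis can still be reported on its own at its planned time. The joint model's T1 estimate may differ slightly from that report, so the plan should say which is definitive.

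**Cost:** some wording and a little programming, with no new data or visits. Four visits need 4 × 5 / 2 = 10 covariance parameters per scale. In the simulations the standard error was about the same as, or slightly smaller than, that of the T2-T4 model.

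The primary Tower of London model is outside this change: five loads at four visits would need 20 × 21 / 2 = 210 covariance parameters from at most 140 people. The definition of the analysis population is also left as it is.

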PD-CFRS	X			X	X	X	X
MRI safety screening	X						
Alcohol abuse screening (CAGE-AID)	X						
Eligibility screening							
Montreal Cognitive Assessment		X		X	X	X	X
ICD diagnostic criteria	X			X			
SAPS-PD [†]	X						
Beck depression inventory		X		X	X	X	X
Hoehn & Yahr stage	X					X	X
Enrolment and allocation							
Intervention							
Cognitive training				↔↔			
Active control condition				↔↔			
Assessments							
Neuropsychological assessment							
1 Tower of London		X		X	X	X	X
Montreal Cognitive Assessment [†]			X	X	X	X	X
Pentagon copy	X		X	X	X	X	X
1/2 Stroop Color Word Test	X		X	X	X	X	X
1 COWAT ('letter fluency') [†]	X		X	X	X	X	X
2 WAIS-III digit span	X		X	X	X	X	X
3 Rey Auditory Verbal Learning Test [‡]	X		X	X	X	X	X
3 Location Learning Test [#]	X		X	X	X	X	X
4 Boston naming test	X		X	X	X	X	X
4 Category fluency	X		X	X	X	X	X
5 Rey Complex Figure Test	X		X	X	X	X	X
5 Visual Form Discrimination Test	X		X	X	X	X	X
Questionnaires and interviews							
CFQ		X		X	X	X	X
Apathy scale	X		X	X	X	X	X
Parkinson anxiety scale	X		X	X	X	X	X
QUIP-RS	X		X	X	X	X	X
NZPAQ-SF	X		X	X	X	X	X

Credibility/expectancy questionnaire	X				
Motor symptom assessments					
UPDRS-III - motor score	X			X	X
Medication use					
Levodopa equivalent daily dosage	X	X	X	X	X
Neuroimaging*					
MP-RAGE	X	X			
3D PSIR	X	X			
fMRI - resting state	X	X			
DTI	X	X			

*in a subsample of N = 80.

Parallel forms of the same test are used at consecutive visits if available: †Three parallel forms; ‡Two parallel forms; #One parallel form.

Cognitive domains: ¹Executive functioning, ²Attention and working memory, ³Memory, ⁴Language, ⁵Visuospatial.

Abbreviations: CFQ = Cognitive Failures Questionnaire; COWAT = Controlled Oral Word Association Test; DTI = diffusion tensor imaging; MP RAGE= magnetization-prepared 180 degrees radio-frequency pulses and rapid gradient-echo; (f)MRI = (functional) magnetic resonance imaging; NZPAQ-SF = New Zealand Physical Activity Questionnaire – Short Form; PD-CFRS = Parkinson's Disease – Cognitive Functional Rating Scale; PSIR = phase-sensitive inversion recovery; QPE = Questionnaire for Psychotic Experiences; QUIP-RS = Questionnaire for Impulsive-Compulsive Disorders in Parkinson's Disease – Rating Scale; SAPS-PD: Scale for Assessment of Positive Symptoms for Parkinson's disease; UPDRS = Unified Parkinson's Disease Rating Scale; WAIS = Wechsler Adult Intelligence Scale.

Interventions

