An active control condition is used to correct for the nonspecific cognitive activity that participants in the CT group go through. In the control condition, participants undergo cognitive engagement using three games (i.e. solitaire, trivia questions and hangman) with a total duration of 45 minutes that will sequentially be performed and are hypothesized not to train specific cognitive functions.

Outcomes

Primary outcome

The primary outcome is the efficacy of CT on executive functions, measured by the percentage correct change score on a previously used computerized self-paced version of the Tower of London (ToL) task [29]. The ToL measures several aspects of executive functions, including planning, inhibition, and working memory [61]. This neuropsychological task consists of a model of three pins with different lengths, and three differently colored beads. In this task, the goal is to get from a starting position to a target position in as minimal steps as possible. There are five planning conditions that range in difficulty, with possible solutions ranging from one to five steps (i.e. task-load S1-S5). After nine exercise items with feedback, 100 pseudo-randomized test trials will be presented with a maximum response duration of 45 seconds per trial and no feedback on accuracy.

Secondary outcomes

The secondary outcome measures include (i) subjective cognitive complaints, (ii) cognitive function (other than the ToL) and (iii) structural and functional connectivity and brain network characteristics. All outcomes described below are changes after intervention relative to baseline.

- 1) Subjective cognitive dysfunction change after the intervention will be measured by the Parkinson's Disease Cognitive Functional Rating Scale (PD-CFRS, [62]) score and the Cognitive Failures Questionnaire (CFQ) score at the end of the intervention (T1), and at follow-up (T2, T3, and T4). We use the PD-CFRS questionnaire as a Parkinson-specific and sensitive measurement of subjective cognitive function. This questionnaire will be filled out by the participant and if possible by a caregiver. We will additionally use the CFQ as this measure has been used more frequently and it is more sensitive to small cognitive errors in daily living such as memory problems, absent-mindedness and slips of action[63];
- 2) Cognitive function change after the intervention will be measured by

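### The secondary factor analysis takes in every neuropsychological outcome in Table 2, including the Tower of London, although the secondary cognitive outcome is defined to exclude it

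*Combined protocol and SAP*

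**What the plan says.** The Primary outcome section makes the ToL the primary measure: efficacy on executive functions is "measured by the percentage correct change score on a previously used computerized self-paced version of the Tower of London (ToL) task". The Analysis Plan models it "using the accuracy on the five separate task-loadings (S1-S5) of the ToL at post-training visit (T1) as dependent measures".

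The Secondary outcomes section then lists, as its second item, "cognitive function (other than the ToL". One way of measuring that item is change on latent factors from the neuropsychological battery, for which the text points to Table 2 and to the analysis section.

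The Analysis Plan describes that analysis: "We will perform a factor analysis on all neuropsychological assessment outcomes (see Table 2) at baseline". Follow-up trait scores are computed from the baseline solution, and the training effect is tested in a multivariate mixed model "using the trait scores as dependent variables".

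The first row under Neuropsychological assessment in Table 2 is "1 Tower of London". By the table's key ("¹Executive functioning, ²Attention and working memory, ³Memory, ⁴Language, ⁵Visuospatial"), the 1 marks it as executive. The Stroop (marked executive and attention) and letter fluency are the only other tests marked executive.

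**The concern.** An analyst cannot follow both instructions. One removes the ToL from the secondary cognitive outcome. The other builds the variables for that outcome from a list that contains it.

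If the Analysis Plan is followed to the letter, a gain on the ToL alone moves a trait score even when no other test has changed. Such a pattern is not far-fetched: Table 3 includes a game whose listed loading is planning, and the Primary outcome section says the ToL measures planning. In the other direction, if training helps other tests but not the ToL, including the ToL dilutes the trait and lowers the chance of seeing that benefit.

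The plan also does not say whether a ToL total or the five task loads S1-S5 would enter. That choice changes what the trait means, and it is left open.

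**Working it through.** **Text comparison.** Secondary outcomes: cognition without the ToL. Analysis Plan: all Table 2 neuropsychological outcomes. Table 2: the ToL is one of them. Neither the latent-factor item under Secondary outcomes nor the factor-analysis text in the Analysis Plan repeats the exclusion. The conflict is in the current text and holds whatever the loadings are.

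**The plan's own figure.** The plan gives no figure for the overlap. Its sample size of 112 is not in dispute and reproduces. For the within-between interaction of a repeated-measures ANOVA with f = .12, two measurements and r = .6, the noncentrality is .12² × 112 × 2 / (1 − .6) = 8.06. On 1 and 110 degrees of freedom at alpha .05, power is .80. Taking the ToL out of the factor analysis changes neither 112 nor 140.

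**Inputs for the illustration.**
- From the Sample size section: effect .23, pre-post r = .6, 140 patients less 10% drop-out = 126.
- Assumed: a one-factor model, loadings of .6 (so tests correlate .36), regression factor scores, a larger ToL effect of .50 SD, a two-sided test at .05, and each trait tested singly.

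**Formulas.** With loadings λ, correlation matrix R and test effects d, the weights are w = R⁻¹λ and the trait shift is w′d / √(w′Rw). With k equal loadings of .6, this becomes (sum of the effects) / √(k + k(k − 1) × .36). The test statistic has mean z = shift / √(1 − .36) × √(126/4) = 7.02 × shift.

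**Effect of .23 / .50 SD on the ToL total only.**
- Three executive tests of Table 2: the ToL carries 1/3 = 33% of the weight. The divisor is √(3 + 6 × .36) = 2.27, so the shift is .10 / .22 SD, z = .71 / 1.54, and rejection is 11% / 34%.
- One of four indicators: weight 25%, divisor √(4 + 12 × .36) = 2.88, shift .08 / .17 SD, rejection 9% / 23%.
- S1-S5 plus three other tests: the effect on the equally weighted ToL total is held at .23 / .50. The five loads sum to an SD of √(5 + 20 × .36) = 3.49, so their effects sum to .80 / 1.75. The divisor is √(8 + 56 × .36) = 5.31, so the shift is .15 / .33 SD and rejection is 19% / 64%.
- Weak ToL loading of .3, three other tests at .6: the weights are .118 for the ToL and .336 for each other test, and √(w′Rw) = .80. The shift is .03 / .07 SD and rejection is about 6% / 8%.

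With the ToL excluded, the rejection rate in all four cases would be 5%, because no other test has moved.

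**Dilution: .23 SD on each of three other tests, none on the ToL.**
- ToL excluded: shift 3 × .23 / 2.27 = .30 SD, power 57%.
- One ToL indicator included: shift 3 × .23 / 2.88 = .24 SD, power 39%.

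**The case against.** The strongest reply is that the Secondary outcomes section sets the scope and the Analysis Plan only gives the method. On that reading the exclusion carries over and the ToL is already out. One can also argue that a latent trait built from many tests is a different measure from the ToL score even when the ToL is one of its indicators. Both readings are possible, but the Analysis Plan states neither. That shows the wording needs settling. It also means that double counting cannot be asserted as fact, only as the result of following the Analysis Plan literally.

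Nothing in the plan uses a trait result to confirm or rescue the primary result. The single-task analyses listed under Exploratory outcomes and covariates would show whether a trait effect came from the ToL alone. This stands as mitigation: the overlap could be detected, but it would still be in the trait score.

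The figures rest on assumed loadings and on testing one trait at a time, whereas the plan specifies a multivariate mixed model. This also stands, so they show a possible range and do not predict a result.

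Two stronger readings are tempting. A reader might infer that the trial's error rate or its primary conclusion is compromised. The documents do not support this, since the primary model does not use the trait scores. A reader might also apply .50 SD to each of S1-S5 and obtain a rejection rate of 91%. That assumes a larger effect on the ToL total than the other scenarios do; with the total held fixed the figure is 64%. On the same basis, a trait made of S1-S5 alone simply moves by the ToL effect itself, .23 or .50 SD.

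**Conclusion.** The two sections conflict, and the conflict should be resolved before analysis. Taken literally, the Analysis Plan puts the primary measure into at least one secondary trait score, mainly the trait or traits on which the ToL loads. Such a trait is not the outcome defined under Secondary outcomes, and a positive result on it would not be evidence separate from the primary result.

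The size is uncertain. Under the stated assumptions, the chance of a significant trait from a ToL-only effect runs from about 6% (weak loading, .23 SD) to 64% (S1-S5 entered, .50 SD). For the three tests that Table 2 marks executive it is 11% to 34%. The loss in the other direction is from 57% to 39% power in the example. The documents do not give the loadings, the number of factors or the ToL score to be used. The consequence is limited to interpretation of the secondary cognitive outcome.

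**What to change.** State in the Analysis Plan that the factor analysis and all trait scores, at baseline and at follow-up, exclude every ToL variable (the total and S1-S5), in line with the Secondary outcomes section. If a version with the ToL is wanted, label it as a sensitivity analysis and say which ToL score enters.

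This is a change of wording and needs no new data or patients. It has one real cost: by Table 2, only the Stroop, which is shared with attention, and letter fluency then remain marked executive. A separate executive trait may be less well determined, and the plan should acknowledge this.
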